**4.2 JUSTIFICATION FOR DOSE**

The dose of 150 mg twice daily is based on the safety and efficacy of fostamatinib from others trials. For chronic immune thrombocytopenia fostamatinib is initially started at a dose of 100 mg twice daily and up titrated to a maximum dose of 150 mg twice daily to achieve the goal of platelets above  $50 \times 10^9/L$  while utilizing lowest possible dose to achieve that goal. Because the treatment duration of fostamatinib in this study may be only 14 days and we are interested in inhibition of the dysregulated immune response, we will start the study drug at the higher dose of 150 mg twice daily.

## **5 STUDY POPULATION**

Subject Inclusion and Exclusion Criteria will be reviewed as appropriate by a member of the study team. If there is any uncertainty, the PI should make the decision on whether a potential subject is eligible for study enrollment. There is no exclusion for receipt of SARS-CoV-2 vaccine (experimental or licensed).

### **5.1 INCLUSION CRITERIA**

1. Patient must be hospitalized, or had their inpatient stay extended, for COVID-19.
2. Age  $\geq 18$  years
3. Subject (or legally authorized representative) provides informed consent prior to initiation of any study procedures.
4. Subject (or legally authorized representative) understands and agrees to comply with planned study procedures.
5. Females of childbearing potential must agree to be abstinent or use a medical acceptable form of contraception from the time of enrollment through 30 days after last day of study drug
6. Laboratory confirmed SARS-CoV-2 RT-PCR test within 7 days of enrollment
7. Illness of any duration with SpO2 of less than 94% on room air requiring supplemental oxygen via nasal canula or non-invasive mechanical ventilation, or mechanical ventilation or ECMO (5 to 7 on the 8-point scale)

### **5.2 EXCLUSION CRITERIA**

1. ALT or AST  $> 5$  times the upper limit of normal (ULN) or ALT or AST  $\geq 3 \times$  ULN and total bilirubin  $> 2 \times$  ULN.  
Estimated glomerular filtration rate (eGFR)  $< 30$  ml/min
2. Pregnancy or breast feeding
3. Anticipated discharge in the next 72 hours
4. Allergy to study medication
5. Uncontrolled hypertension (systolic blood pressure  $> 160$  mmHg or diastolic blood pressure  $> 100$  mmHg)
6. Shock or hypotension at the time of enrollment
7. Neutrophil count  $< 1000/\mu\text{L}$
8. Concern for bacterial or fungal sepsis
9. Received immunomodulatory treatment within 30 days prior to enrollment e.g., Bruton's tyrosine kinase/phosphoinositide 3 kinase/Janus kinase inhibitor or cytokine-targeting biologic therapy (anti-TNF, IL-6), or B-cell depleting antibody in the prior 6 months (rituximab, other anti-CD20 mAb)
10. Received a live vaccine the last 4 weeks
11. Those who were cognitively impaired or mentally disabled prior to COVID diagnosis

#### **1.1 INCLUSION OF VULNERABLE PARTICIPANTS**

12. Participation in another clinical trial for the treatment of COVID-19.

### **5.3 INCLUSION OF VULNERABLE PARTICIPANTS**

Certain human subjects are categorized as vulnerable populations and require special treatment with respect to safeguards of their well-being. For this clinical trial, examples include intubated individuals who are sedated. When it is determined that a potential research subject is cognitively impaired, federal and institutional regulations permit researchers to obtain consent from a legally authorized representative (LAR). The study team will obtain consent from these vulnerable subjects using an IRB-approved protocol- specific process for consent using a LAR.

For subjects for whom a LAR gave consent, during the course of the study, if the subject regains the capacity to consent, informed consent must be obtained from the subject and the subject offered the ability to leave the study if desired.

It is particularly important to include patients who may be sedated while on mechanical ventilation or extracorporeal membrane oxygenation because they are they patients who have suffered the most severe complications of this disease.

### **5.4 LIFESTYLE CONSIDERATIONS**

Study participant should refrain from drinking alcohol while taking study drug.

Once discharged, subjects of child bearing potential should avoid pregnancy through abstinence or use of at least one contraceptive until 30 days after last day of study drug.

### **5.5 SCREEN FAILURES**

Screen failures are defined as participants who consent to participate in the clinical trial but are not subsequently assigned to the study intervention or entered in the study because the participants did not meet the trial eligibility or withdrew consent. A minimal set of screen failure information is required to ensure transparent reporting of screen failure participants, to meet the Consolidated Standards of Reporting Trials (CONSORT) publishing requirements and to respond to queries from regulatory authorities. Minimal information includes demography, screen failure details, eligibility criteria, and any serious adverse event (SAE).

Individuals who do not meet the criteria for participation in this trial (screen failure) may be rescreened once. Rescreened participants should be assigned the same participant number as for the initial screening.

### **5.6 STRATEGIES FOR RECRUITMENT**

This is a multi-site study and subjects will be enrolled at the NIH Clinical Center, Inova Fairfax and Alexandria hospitals. Hospitalized participants will be recruited from within NIH and from the Inova hospitals.

A written strategic recruitment plan will be authored by the NHLBI Patient Recruitment Office (PRO) and ongoing regular recruitment-focused meetings will be held with the PRO and study staff and partners to ensure the study is meeting enrollment projections. If enrollment projections

*Abbreviated Title: Fostamatinib for COVID*

*Version Date: 09/17/2020*

are not being met, a strategy to boost enrollment will be implemented, and may include local news media coverage and live social media events.

Source of participants include inpatient hospital setting, outpatient clinics, and general public. The participants may also be recruited via self-referral, from in-patient services of regional hospitals and from outpatient settings.

Participants may be recruited through the use of:

- Flyers, documents/info cards, etc. for in-hospital use with patients and family;
- Recruitment advertisements and writeups placed in the NIH Record, NIH websites, the Clinical Center News;
- ResearchMatch.org;
- Newspaper writeups (print and digital) in local newspapers or outlets;
- NIH email listservs;
- Media interviews with investigators;
- NIH social media on Facebook and/or Twitter;
- ClinicalTrials.gov, Clinical Center “Search the Studies” website, NHLBI website, and NIH CC study recruitment page facilitated by CC communications office;
- Paid, targeted advertising, including digital social media ads, to local public population may be done led by the NHLBI digital communications specialist.
- A letter to physicians about the study may be provided to area ICUs and hospitalist groups.
- Hospital partners will be provided with written study materials, and in-service sessions by the study PI to educate and inform about the study.

There are no restrictions based on gender, race or ethnicity, or non-English speaking subjects.

All advertising/recruitment language will be IRB reviewed/approved prior to posting/using. Recruitment materials may be translated from English into other languages, including Spanish. Anticipated accrual rate is approximately 25 patients per month.

### **5.6.1 Costs**

There are no costs associated to this study for subjects treated at the NIH.

By virtue of NHLBI sponsorship of clinical research protocols, enrolling sites qualify for Centers for Medicare and Medicaid Services (CMS) coverage of associated routine costs of medical care under the CMS Clinical Trial Policy (CTP). This policy is detailed at <https://www.cms.gov/Medicare/Coverage/ClinicalTrialPolicies/index.html>. According to this policy, CMS is explicitly authorized to provide payment for routine patient care costs and costs due to medical complications associated with participation in clinical trials.

### **5.6.2 Compensation**

Study subjects will be compensated for outpatient phlebotomy and follow up visits that occur at the NIH as follows:

- \$50 for each blood draw;

- \$20 for your first hour, and \$10 for each subsequent hour spent at NIH Clinical Center during the follow up visit.

## **6 STUDY INTERVENTION**

### **6.1 STUDY INTERVENTIONS(S) ADMINISTRATION**

All patients will be randomized to receive fostamatinib or matching placebo. All patients will receive standard of care.

#### **6.1.1 Study Intervention Description**

Patients hospitalized with COVID-19 on oxygen will receive fostamatinib at a dose of 150 mg twice daily for 14 days or placebo. Patients who are discharged prior to completing a 14 day course will continue therapy as an outpatient.

Fostamatinib is a spleen tyrosine kinase inhibitor that is currently FDA approved for the treatment of thrombocytopenia in adult patients with chronic immune thrombocytopenia (ITP) who have had an insufficient response to a previous treatment.

The use of fostamatinib for the proposed indication is investigational and the study will be conducted under FDA IND #152131.

Fostamatinib is a prodrug with an active metabolite, R406, which is known to inhibit Fc-activating receptors and B-cell receptors. R406 is protein bound and has a half-life of 15 hours, with 80% of excretion occurring in feces and 20% excreted in urine.

Concomitant use with strong CYP3A4 inhibitors with fostamatinib will increase exposure to R406 that may result in increased risk of adverse reactions while concomitant use of strong CYP3A4 inducers reduces exposure to R406. Fostamatinib may increase the concentration of some CYP3A4 substrate drugs, some BCRP substrate drugs (ex. rosuvastatin), and some P-glycoprotein substrate drugs (eg. Digoxin).

#### **6.1.2 Dosing and Administration**

All patients will start fostamatinib or matched placebo at a dose of 150 mg orally twice daily for a total of 14 days (28 scheduled doses) to be swallowed as an oral tablet. If necessary, tablets can be crushed until granular with an approximate particle size <2 mm, added to approximately 10 mL of water, and stirred to mix before administration through the orogastric or nasogastric tube. Dose modifications based on adverse reactions are described in section 6.1.2.3

##### **6.1.2.1 Dose Escalation**

N/A

##### **6.1.2.2 Dose Limiting Toxicity**

N/A

##### **6.1.2.3 Dose Modifications**

Adverse Reaction	Recommended action
Hypertension	

*Abbreviated Title: Fostamatinib for COVID*

*Version Date: 09/17/2020*

Stage 1: systolic between 130-139 or diastolic between 80-89 mmHg	Initiate or increase antihypertensive medication for patients with increased risk of cardiovascular risk, and adjust as needed. No dose modification to study drug required.
Stage 2: systolic at least 140 or diastolic at least 90 mmHg	Initiate or increase antihypertensive medication and adjust as needed until BP control. No dose modification to study drug required.
Hypertensive crisis: systolic over 180 and or diastolic over 120 mmHg	Discontinue study drug until blood pressure is below systolic blood pressure of 160 and diastolic less than 100 mmHg. When restarting study drug dose should be reduced to 100 mg twice daily or matching placebo for the remainder of the study
Hepatotoxicity	
Increase in AST/ALT by x3 from level at the time of enrollment	Stop study drug and recheck liver function tests the next day. May restart when AST/ALT have returned to less than 3x baseline. When restarting study drug dose should be reduced to 100 mg twice daily or matching placebo for the remainder of the study*
Increase in AST/ALT to 3X ULN and total BL (bilirubin) greater than 2 x upper limit of normal (ULN)	Stop fostamatinib and recheck liver function tests the next day. May restart when AST/ALT have returned to less than 3x ULN and total BL has returned to less than 2x upper ULN. When restarting study drug dose should be reduced to 100 mg twice daily or matching placebo for the remainder of the study*
Elevated unconjugated (indirect) BL in absence of other LFT abnormalities	Continue study drug with frequent monitoring since isolated increase in unconjugated (indirect) bilirubin may be due to UGT1A1 inhibition
Diarrhea	
Diarrhea	Manage diarrhea using supportive measures (e.g., dietary changes, hydration and/or

	antidiarrheal medication) early after the onset until symptoms resolve.  If symptoms become severe (grade 3) or above), temporarily stop study until symptoms resolve to mild (grade 1). When restarting study drug dose should be reduced to 100 mg twice daily or matching placebo for the remainder of the study
Neutropenia	
Neutropenia	If absolute neutrophil count decreases (ANC less than $1.0 \times 10^9/L$ ) discontinue fostamatinib. When ANC returns to above $1.0 \times 10^9/L$ , restart study drug. When restarting study drug dose should be reduced to 100 mg twice daily or matching placebo for the remainder of the study

\*Parameters and laboratory abnormalities must resolve within 3 days to restart the study drug.

#### 6.1.2.4 Drug Administration

Study drug may be taken with or without food. In the case of a missed dose of study drug subjects should take their next dose at its regularly scheduled time. For patients able to swallow medication should be taken orally. For patients who are unable to swallow, on mechanical ventilation or on EMCO drug should be crushed and provided via nasogastric or orogastric access. Tablets should be crushed until granular with an approximate particle size  $<2$  mm, added to approximately 10 mL of water, and stirred to mix before administration through the orogastric or nasogastric tube

If a subject is discharged from the hospital and then readmitted prior to Day 14, they may be given the remainder of the same study product up until day 14 that they were taking as an outpatient already. If the subject did not withdraw his/her consent to participate in the study, there is no need to re consent upon readmission to the study hospital. The study team will need to notify the study pharmacist of the readmission. No study medication should be given past Day 14 (total 28 doses).

## 6.2 PREPARATION/HANDLING/STORAGE/ACCOUNTABILITY

### 6.2.1 Acquisition and Accountability

Investigational product (IP) will be shipped to the site either directly from Rigel Pharmaceuticals, or from other regional or local drug repositories. All other supplies should be provided by the site. Multiple lots of IP may be supplied.

*Abbreviated Title: Fostamatinib for COVID*

*Version Date: 09/17/2020*

Study products received at the sites will be open label unless specified in the protocol-specific pharmacy manual. Drug preparation will be performed by the participating site's unblinded research pharmacist on the same day of administration to the subject.

The site PI is responsible for study product distribution and disposition and has ultimate responsibility for study product accountability. The site PI may delegate to the participating site's research pharmacist responsibility for study product accountability. The participating site's research pharmacist will be responsible for maintaining complete records and documentation of study product receipt, accountability, dispensation, storage conditions, and final disposition of the study product(s).

### **6.2.2 Formulation, Appearance, Packaging, and Labeling**

Fostamatinib will be provided by Rigel Pharmaceuticals and stored in the pharmacy of each participating hospital. The drug product consists of 2 strengths of orange film-coated, plain, bioconvex tablets. The 150 mg tablet is oval and the 100 mg tablet is round. The tablets are supplied in white opaque high-density polyethylene bottles capped with white polypropylene child resistant closures with foil induction seals. Placebo tablets to match fostamatinib 100 mg and 150 mg will be provided by Rigel.

### **6.2.3 Product Storage and Stability**

Store at room temperature, 20°C to 25°C (68°F to 77°F); excursions permitted between 15°C to 30°C (59°F to 86°F). Do not remove desiccants.

### **6.2.4 Preparation**

For patients who are unable to take oral medication tablets should be crushed until granular with an approximate particle size <2 mm, added to approximately 10 mL of water, and stirred to mix before administration through the orogastric or nasogastric tube

## **6.3 MEASURES TO MINIMIZE BIAS: RANDOMIZATION AND BLINDING**

### **6.3.1 Randomization**

The study will randomize subjects 1:1 to placebo or fostamatinib. Once a subject has completed the screening and baseline period and evaluation for inclusion/exclusion criteria, the randomization process will begin. The site investigator or designee will obtain the randomized assignment for that subject from the data coordinating center. Randomization will be stratified by site and severity of illness at enrollment. Severity of illness will be stratified into ordinal scale 5 and 6 (supplemental oxygen via nasal canula or non-invasive ventilation), mechanical ventilation, and ECMO.

### **6.3.2 Blinding and Masking Procedures**

As both arms are receiving standard of care, the product for standard of care is not blinded.

*Abbreviated Title: Fostamatinib for COVID*

*Version Date: 09/17/2020*

The fostamatinib and matched placebo is blinded. Fostamatinib and placebo tablets are identical in appearance.

Unblinding of the study will occur after all subjects enrolled have reached the end of study, and these visits are monitored and data is cleaned, or if the DSMB recommends unblinding.

If AEs occur and investigators are concerned about the treatment allocation, the treatment can be discontinued. If a Serious Adverse Event occurs, that is thought to be related to the study drug, and the treating clinician believes that knowledge of the treatment arm may change the therapy provided to the patient, the individual subject can be unblinded

#### **6.4 STUDY INTERVENTION COMPLIANCE**

During the inpatient phase of the study each dose of study product will be administered by a member of the clinical care team who is qualified and licensed to administer the study product. Administration, date, and time will be entered into the appropriate case report form (CRF). If a patient is discharged prior to day 14, study drug supply will be given to the patient to be taken at home up until day 14, for a total of 28 doses. The participant compliance will be monitored by pill counts at the day 15 visit. If this visit takes place remotely via telehealth, the investigator will observe the research subject counting the remaining pills. The quantity of taken drug, date, and time will be entered into the appropriate case report form (CRF).

#### **6.5 CONCOMITANT THERAPY**

For this protocol, a prescription medication is defined as a medication that can be prescribed only by a properly authorized/licensed clinician. Medications to be reported in the CRF are concomitant prescription medications, over-the-counter medications and supplements used for the treatment of COVID-19.

For patients that are eligible for the study, other therapy received prior to enrollment with any other experimental treatment or off-label use of marketed medications that are intended as specific treatment for COVID-19 or the SARS-CoV-2 infection not identified in the exclusion criteria are permitted but must be discontinued on enrollment.

In patients who have clinical deterioration while on fostamatinib any rescue or investigational therapy that a provider thinks may benefit a patient may be administered (e.g. tocilizumab and convalescent plasma). Administration of these drugs will be tracked via the CRF.

Venous thromboembolism (VTE) prophylaxis is recommended for all patients unless there is a major contraindication such as active bleeding events or history of heparin-induced thrombosis.

Concomitant medications will be assessed only from 7 days prior to enrollment through discharge. Report all prescription medications taken during this time period.

*Abbreviated Title: Fostamatinib for COVID*

*Version Date: 09/17/2020*

Do not report vitamins, herbal supplements, or topical medications. Do not report over-the-counter cold medicines and antipyretics that the subject reportedly took at home prior to hospitalization.

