## 4 STUDY DESIGN

### 4.1 OVERALL DESIGN

We intend to study fostamatinib for the treatment of hospitalized patients with COVID-19.

- This will be a multicenter, randomized, double-blind, placebo-controlled, phase 2 trial with the objective to evaluate the safety of fostamatinib compared to matching placebo in COVID-19 patients who are hospitalized with a 5, 6, or 7 on the 8-point ordinal scale.
- The NHLBI will be the Coordinating Center for this multicenter study. All participating sites will enroll and treat subjects as described below. Research labs for exploratory endpoints will be processed at participating sites or shipped to the NIH Clinical Center for processing.
- All study participants will receive standard of care throughout the entire study and then will be randomized to 150 mg of fostamatinib twice a day or placebo for 14 days (total 28 doses).
- Subjects will be assessed daily while hospitalized and followed until day 60. If patients improve and are discharged prior to day 14 the study drug will be continued until day 14 as an outpatient. Patients who are discharged on study drug will receive a phone call daily to assess for adverse events and will have safety labs drawn on days 3, 5, 8, 11 as applicable (outpatient third party lab acquisition may be utilized as needed). We will make every effort to bring back discharged patients for outpatient visits on days 15, 22, 29, and 60 to include laboratory draws. In patients who are unable to follow-up, they will receive a telephone visit as a follow up.
- Day 1 of study is the first day of study drug and patients will be followed until day 60.

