### **9.3.7 Sub-Group Analyses**

The following subgroups analysis will be performed.

- Symptoms duration >10 and ≤10 days
- Baseline disease severity
- Race (White, Black, Asian)
- Age (18 to <40, 40 to <66, ≥65)
- Sex (male and female)
- Concomitant therapies (e.g. treatment with and without remdesivir, steroids (dexamethasone, prednisone, hydrocortisone, methylprednisolone), convalescent plasma, tocilizumab or other immunomodulators intended for the treatment of COVID-19)
- Therapy with anti-coagulation by dose

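### Medication recording stops at discharge while study drug continues at home to Day 14, so drugs started or changed during home dosing are not systematically captured

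*Combined protocol and SAP*

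**What the plan says.** Section 6.5 (Concomitant Therapy) sets the window: "Concomitant medications will be assessed only from 7 days prior to enrollment through discharge". It then says: "Report all prescription medications taken during this time period". A separate paragraph of 6.5 deals with rescue or investigational treatment after deterioration on fostamatinib: "Administration of these drugs will be tracked via the CRF". That sentence has no end date and is not tied to discharge.

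Dosing does not end at discharge. Section 4.1: "If patients improve and are discharged prior to day 14 the study drug will be continued until day 14 as an outpatient". Section 6.4: "study drug supply will be given to the patient to be taken at home up until day 14, for a total of 28 doses". Section 6.1.2.4 foresees readmission before Day 14 with the same study product, but neither it nor 6.5 says whether medication recording starts again.

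The primary endpoint is the cumulative incidence of SAEs through Day 29 (Sections 3 and 9.1). Section 8.4.4 collects SAEs to Day 60.

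On interactions, Section 6.1.1 warns: "Concomitant use with strong CYP3A4 inhibitors with fostamatinib will increase exposure to R406 that may result in increased risk of adverse reactions". It adds that fostamatinib may raise the concentrations of some CYP3A4, BCRP and P-glycoprotein substrates. Section 8.4.3.2 makes other drugs part of the causality grading.

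**The concern.** The medication window is shorter than both the exposure window and the endpoint window. During home dosing the patient has left the setting where prescribing is visible to the enrolling hospital. Under Section 8.2, outpatient assessment moves to the NIH Clinical Center, in person or remotely, whichever site enrolled the patient. A new outpatient prescription in that period could change exposure to the active metabolite, have its own exposure changed, or cause an event itself. The plan has no routine place to record it.

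Safety is the primary objective, so the record behind each event matters. Three things are at stake: the investigator's causality grade (Section 8.4.3.2), the planned summary of related AEs (Section 9.3.4), and the reading of any SAE imbalance. There is also a plainer case. For raised blood pressure short of crisis, the dose-modification table in Section 6.1.2.3 has antihypertensive treatment started or increased with no change to study drug. If that happened at home, the medication record would not show it.

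**Working it through.** The plan gives no figure to reproduce here. The sample size of about 60 rests on feasibility (Section 9.1), and no power or alpha value is involved. The check has two parts.

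**1. Does anything else extend the recording?** Places where it might:

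- Schedule of Activities (1.3): there is no concomitant-medication row. The note on contacts after discharge lists adverse events, ordinal status, readmission and mortality.
- Daily calls to patients discharged on study drug (4.1 and 8.3): their stated purpose is adverse events.
- Data items for each AE (8.4.4): description, onset, severity, relationship and resolution. Medications are not listed.
- SAE reporting (8.4.6): supporting documents may be requested, which is ad hoc.
- Rescue therapy (6.5): tracked in the CRF with no stated end date. This is an exception for that class of treatment, not for newly prescribed drugs in general.

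None of these makes routine medication recording continue after discharge.

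**2. How long is the gap in the dosing period?** Inputs are 14 dosing days at two doses a day, 28 doses in all (4.1, 6.4). Let *d* be the discharge day, taken as the last day covered.

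- Dosing days without updated recording = max(0, 14 − *d*).
- Doses affected = 2 × max(0, 14 − *d*).

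The documents give no distribution of discharge day. Days 5, 8 and 11 are used as assumptions because the plan schedules outpatient contacts on those days. Day 14 is added as the boundary.

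| Discharge day (assumed) | Dosing days not covered | Share of 14 | Doses of 28 |
|---|---|---|---|
| 5 | 14 − 5 = 9 | 64% | 18 |
| 8 | 14 − 8 = 6 | 43% | 12 |
| 11 | 14 − 11 = 3 | 21% | 6 |
| 14 or later | 0 | 0% | 0 |

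The interaction concern outlasts the last dose only briefly. With the 15-hour half-life in Section 6.1.1, five half-lives are 5 × 15 = 75 hours, about 3 days, which reaches about Day 17. From then to Day 29 the issue is no longer interaction but other treatments as competing explanations for a late SAE.

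**The case against.** The strongest reply is that the limit looks deliberate, a way to contain data burden in a small feasibility-sized trial, and that an individual SAE would not go unexplained. Investigators must weigh other drugs when they grade causality. Patients on home dosing are called daily, a readmission would usually itself qualify as an SAE, and supporting documents can be requested. This is fair as far as it goes. It shows that information can be found for a given event. It does not show that it is gathered consistently, or at all for patients without an SAE, who are the comparison needed to judge whether a co-medication explains an imbalance.

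A reader might infer more than the documents support:

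- **That the primary comparison is compromised.** It is not. Section 9.3.2 compares SAE percentages by Fisher's exact test, regardless of cause, and no medication data enter it.
- **That rescue therapy after discharge goes unrecorded.** Section 6.5 tracks rescue therapy after deterioration on study drug separately, with no cut-off at discharge.
- **That treatment on readmission is excluded.** The text is silent on this, so the position is unclear.
- **That the subgroups in Section 9.3.7 are misclassified.** The therapies named there are mainly inpatient ones, which are recorded. For "Therapy with anti-coagulation by dose", inpatient use is recorded too, and nothing defines the subgroup by use after discharge. Classifying patients by drugs started later would also condition on events after randomization.
- **That the whole period from discharge to Day 29 is an interaction gap with no medication data.** Drugs already in use at discharge are on record. What is missed is later change, and the interaction concern fades at about Day 17.

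**Conclusion.** The point holds in a limited form. By its own rule the plan stops systematic medication recording at discharge while some patients are still being dosed, and no other section makes up for it. The loss falls on causality grading, the related-AE summary and the interpretation of any SAE difference, not on the primary test.

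Its size depends on when patients go home: 9, 6 or 3 of 14 dosing days for assumed discharge on Day 5, 8 or 11, and none for patients in hospital through Day 14. These are calendar days per discharged patient. They are not counts of patients, interactions or SAEs, none of which the documents allow one to estimate. The population includes ventilated and ECMO patients, and patients expected to leave within 72 hours are excluded, so a share of those enrolled will have a short gap or none. Patients still in hospital at Day 29 have no gap in the primary window either.

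This is a gap in data collection, not a numerical error. It is worth closing because these data may be hard to recover afterwards.

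**What to change.** In Section 6.5, replace the cut-off at discharge with two rules, applied alike in both arms:

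1. For patients discharged on study drug, record prescription medications started, stopped or changed through the Day 15 visit.
2. For any readmission or SAE through Day 29, record prescription medications around that event, and state expressly that recording resumes on readmission.

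Collect this at the daily on-drug calls and the Day 15, 22 and 29 contacts, and add a matching row to the Schedule of Activities. With the first rule, uncovered dosing days become 0 for any discharge day. The second rule covers late SAEs without a full log for every patient to Day 29.

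The cost is modest extra data entry. Section 10.8.1 already has concomitant medications entered in the data capture system. Sample size, primary test, dosing and visit schedule do not change.
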